## 3.3 Subject Data and Study Conduct

### 3.3.1 *Patient Disposition and Withdrawals*

The following patient disposition categories will be summarized via counts and percentages for all enrolled patients:

- Patients who were enrolled
- Patients who were treated with at least one dose of EDG-5506

- Patients who received all protocol-specified doses of EDG-5506
- Patients who discontinued treatment of EDG-5506
- Patients who completed the study
- Patients who discontinued the study
- Patients with interruption of study drug
- Treatment status (experienced vs. naïve).

Based on availability, patients may roll over to the open-label EDG-5506-203 protocol at a visit prior to Month 24. These patients will be considered as completing EDG-5506-002 and their last study visit in EDG-5506-002 will serve as the final data point. Patients in the SAF who discontinued study drug will be summarized by reason for discontinuation (all reasons) via count and percentage. Patients in the SAF who discontinued from the study will be summarized by reason for discontinuation (all reasons) as recorded on the Case Report Form (CRF) via count and percentage.

### 3.3.2 Demographic and Baseline (BL) Characteristics

The following demographic and BL characteristics will be summarized:

- Age (years)
- Sex
- Race
- Ethnicity
- Height (cm)
- Weight (kg).

Demographic and BL disease characteristics will be summarized with descriptive statistics or counts and percentages, based on the number of participants in the SAF.

### 3.3.3 Medical History

Medical history will be coded to system organ class and preferred term using the Medical Dictionary for Regulatory Activities (MedDRA) version 24.1 or higher. Counts and percentages of patients with medical history by system organ class and preferred term will be summarized. The table and listing will be sorted alphabetically by System Organ Class (SOC) and Preferred Term (PT). Medical history will be listed by patient. The listing will also display the verbatim text from the study investigators.

### 3.3.4 Concomitant Medications

Prior and concomitant medications/therapies will be coded to anatomical therapeutic chemical (ATC) class and preferred term using the World Health Organization (WHO) Drug Dictionary version Sept 2021 B3. For summary purposes, medications will be considered prior medications if they stopped prior to the first dose of study drug and concomitant medications if they were taken at any time after the first dose of study drug (i.e., started prior to the first dose of study drug and were ongoing or started after the first dose of study drug). Counts and percentages of patients taking prior and concomitant medications will be summarized by ATC class and preferred term based on the SAF.

### 3.3.5 *Protocol Deviations*

All protocol deviations will be presented in data listings.

### 3.3.6 *Study Drug Exposure and Compliance*

The extent of exposure to study drug EDG-5506 will be summarized by the following parameters:

- Number of doses administered
- Duration of exposure (in weeks) will be calculated as: [(last dose date of study treatment – first dose date of study treatment) + 1]/7
- Total administered dose
- Total administered dose as a percentage of total planned dose.

The planned dose is defined as the dose that would be given if no doses were missed and/or no dose reductions were made. The total planned dose is the sum of all planned doses.

- Dose discontinued, delayed or interrupted.

Exposure measures will be summarized based on the SAF.

## 3.4 Clinical and Functional Assessments

Unless otherwise stated, clinical and functional analyses will be performed on the SAF.

### 3.4.1 *Functional Assessments*

The CFB for functional assessments will be summarized at each scheduled time point for the following measures:

- NSAA
- NSAD
- Muscle strength test
- Timed function tests (TFTs)
  - 4-stair climb test summarized as both time and velocity (*unit=1/seconds*)
  - 100-meter timed test summarized as both time and velocity (*unit=meters/second*)
  - 10-meter walk run test summarized as both time and velocity (*unit=meters/second*)
  - Rise from supine summarized as both time and velocity (*unit=1/seconds*).

Note that the four TFT endpoints will be transformed from time to velocity (speed) as indicated by the endpoint's units. If a participant is unable to complete the TFT a velocity of "0" will be imputed.

### 3.4.2 *Clinical Outcomes*

The CFB in the following clinical outcomes will be summarized at each scheduled time point:

- Activity limitations (ACTIVLIM)
- Patient-Reported Outcomes Measurement Information System (PROMIS-57).

### 3.4.3 Subgroups

No subgroup analyses or summaries will be performed.

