2.3.1. Risk Assessment

As of May 8th, 2022, 90 healthy adult volunteers and 12 adults with BMD have received at least one dose of EDG-5506. EDG-5506 was well tolerated with no withdrawals due to treatment-related AEs. The most common AEs were dizziness, drowsiness, and blurred vision. These were self-limiting and generally occurred more frequently early in dosing despite continued increase in circulating levels of EDG-5506 later in dosing. No AE in BMD patients resulted in withdrawal or dose-adjustment. There were no SAEs or severe AEs.

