4.1. Overall Design

This is an open-label, single-center, Phase 1b study to assess the safety and PK of EDG-5506 in adults with BMD. This study will enroll participants diagnosed with BMD who completed (through Day 42) the first-in-human study, [EDG-5506-001](#). If necessary, additional participants (treatment naïve) from outside the EDG-5506-001 study may be enrolled to meet the target enrollment of 8 evaluable participants (see [Section 9.2](#) for details).

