9.4.6. Pharmacokinetics

Treatment-experienced participants: Exposures will be summarized using descriptive statistics at each time point collected. Additional PK analysis may be done outside of the clinical study report (CSR).

Treatment-naïve participants: For Day 1, standard PK parameters endpoints will be estimated and summarized using descriptive statistics based on the PK Evaluable Population.

Exposures will be summarized using descriptive statistics at each time point collected. Additional PK analysis may be done outside of the CSR.

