#### 3.5.1.2 AE Summaries

A patient who reported multiple AEs that map to a common PT or SOC is counted only once for that PT or SOC at the highest severity reported and at the greatest relationship to study drug. The number and percentage of subjects who experienced at least one AE will be tabulated by SOC and PT with respect to dose level/treatment group for each study part. The same tabulation will also be applied to any SAE, any AE leading to premature discontinuation from the study, TEAEs and treatment-emergent SAEs.

The number and percentage of patients who experienced at least one AE will also be tabulated by SOC and PT within each dose level/treatment group with respect to relationship to study drug (related, not related) and severity (mild, moderate, severe).

Patient listings will also be provided for all AEs, all SAEs, all AEs leading to early discontinuation from the study and all AEs leading to study drug interruptions. Length of interruptions will also be provided.

An overview of AEs will be provided including counts and percentages of patients with the following:

- Any TEAEs (overall and by maximum severity)
- Any study drug-related TEAEs
- Any serious AEs (SAEs)
- Any TEAEs leading to discontinuation of study drug
- Any TEAEs leading to discontinuation of study

- Any AEs leading to death.

Separate tables including counts and percentages of patients will also be presented by system organ class and preferred term for each of the categories in the overview.

If an AE has incomplete start or stop dates, dates will be imputed to determine whether the AE was treatment-emergent. Details on the imputation for incomplete dates will be provided in the final SAP to correspond to CRF design and instructions.

Patient listings of all AEs will be presented, as well as listings specifically for SAEs and TEAEs leading to discontinuation of study drug.

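### Adverse-event tables are not split by prior EDG-5506 exposure, so pooled incidence depends on the enrolment mix and may understate first-exposure incidence; the PK split set out in the protocol is also missing from the SAP

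*SAP*

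**What the plan says.** On who is studied, Protocol 4.1 says: "This study will enroll participants diagnosed with BMD who completed (through Day 42) the first-in-human study". Treatment-naïve participants from outside may be added to reach about 8 evaluable. Protocol 4.2 says EDG-5506-001 was placebo-controlled. It gives its placebo participants the same extra on-site dosing day as outside naïve participants.

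On the adverse-event pattern, Protocol 2.3.1 names dizziness, drowsiness and blurred vision as the most common events, and says they "generally occurred more frequently early in dosing despite continued increase in circulating levels of EDG-5506 later in dosing".

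On analysis, SAP 3.3.1 counts treatment status (experienced or naïve) in the disposition summary. SAP 3.5.1.2 has adverse events "tabulated by SOC and PT with respect to dose level/treatment group for each study part"; prior exposure is not mentioned. SAP 3.4.3 reads "No subgroup analyses or summaries will be performed". No table in SAP Appendix A is described as split by status.

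On PK, Protocol 9.4.6 writes the two groups up separately: "Treatment-experienced participants: Exposures will be summarized using descriptive statistics at each time point collected". For naïve participants it adds Day 1 PK parameters. SAP 3.6 and Table 14.4.1.1 plan only summaries of concentrations, with no mention of status.

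**The concern.** The primary endpoint is the incidence, frequency and severity of adverse events. If those events depend on time since first exposure, a participant who already had 14 days of EDG-5506 may report fewer of them than a first-time user. One pooled percentage then averages two different quantities, weighted by an enrolment mix that the protocol leaves open. A reader who wants to know what happens at first exposure could not recover it from the planned tables.

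Dose level cannot stand in for status, because all participants follow the same planned dose sequence (SAP 2.4). The plan already records the status that would be needed; it just does not use it in the adverse-event output.

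**Working it through.** There is no planned calculation to reproduce. Protocol 9.2 sets the target of about 8 empirically, with no event rate, precision or power behind it.

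**1. Possible mix.** Adults with BMD exposed before this study: 5 (Protocol 4.2). Exposed by 8 May 2022: 12 (Protocol 2.3.1). So at least 12 − 5 = 7 were first exposed after EDG-5506-001. At most 5 participants can be experienced. Two scenarios follow, both assumptions: 5 experienced + 7 naïve (all 12 are in this study), and 5 + 3 (the target of 8). Fewer experienced participants in a study of the same size would bring the pooled value closer to the naïve one.

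**2. Effect of pooling.** With r the experienced rate divided by the naïve rate,

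pooled / naïve = (n_exp × r + n_naïve) / (n_exp + n_naïve).

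The documents give no rate by status, so r is assumed to run from 0.25 to 1.25. Example for r = 0.25: (5 × 0.25 + 7)/12 = 8.25/12 = 0.69, and (5 × 0.25 + 3)/8 = 4.25/8 = 0.53.

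| r | 5 + 7 | 5 + 3 |
|---|---|---|
| 0.25 | 0.69 | 0.53 |
| 0.5 | 0.79 | 0.69 |
| 1.0 | 1.00 | 1.00 |
| 1.25 | 1.10 | 1.16 |

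At an assumed naïve rate of 50%, pooled incidence runs from 34.4% to 55.2% (5 + 7) and from 26.6% to 57.8% (5 + 3). It is too low only if r is below 1.

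**3. Is r below 1?** Exclusion criterion 10 requires 30 days or 5 half-lives off investigational drug, whichever is longer. With the 7-day half-life in BMD (Protocol 4.2), that is 5 × 7 = 35 days, leaving 2^(−5), about 3%, of the drug. Experienced participants therefore also restart from near zero. The documents do not say whether tolerance outlasts such a break.

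**4. What a split can resolve.** Exact 95% intervals: 4/7 gives 18.4% to 90.1%; 2/3 gives 9.4% to 99.2%; 1/5 gives 0.5% to 71.6%. For comparison, a pooled 4/8 gives 15.7% to 84.3%. At assumed rates of 25% against 50%, a two-sided Fisher test reaches p ≤ 0.05 with probability about 6% (5 against 7) or 3% (5 against 3). A split can only be descriptive.

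**5. PK, side by side.** Protocol 9.4.6 gives exposures by time point under each status heading, plus Day 1 parameters for naïve participants. SAP 3.6 gives concentration summaries and listings only. SAP section 5 says nothing deviates from the protocol. It measures itself against Amendment 4, whereas the protocol supplied is a later amendment; in either case the SAP and the current protocol differ.

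**The case against.** Several points on the other side stand.

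- **Scope of the subgroup rule.** A reader might infer that the SAP forbids any adverse-event split. Section 3.4.3 sits under 3.4, whose opening sentence is about functional work: "Unless otherwise stated, clinical and functional analyses will be performed on the SAF". Safety has its own section, 3.5. For adverse events the accurate statement is that no split is planned. The sentence in 3.4.3 is worded without limit, however, so it should be reconciled.
- **Direction of bias.** A reader might infer that the pooled figure does understate first-exposure incidence. That needs a lower rate in experienced participants after a washout, which the documents do not show.
- **Selection.** A reader might infer that the experienced group was selected for tolerating the drug. Protocol 2.3.1 reports no withdrawals due to treatment-related events, which gives that little support.
- **Partial remedy in place.** "Patient listings will also be provided for all AEs, all SAEs", and SAP 3.1.7 calculates time since first dose for treatment-emergent events. With roughly 8 to 12 participants, a reader could make the split by hand. That works only if status can be linked to each participant, and no listing in Appendix A is specified as showing it.
- **A naïve column alone is not first-exposure incidence.** Over up to 24 months at changing doses it also collects late events. This is correct, and is why an early-onset display is needed.
- **PK is a separate matter.** Protocol 9.4.6 may separate the groups largely because only naïve participants have serial Day 1 sampling, so it is not evidence about adverse events. The mismatch with SAP 3.6 remains.

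**Conclusion.** The point holds as a cheap improvement to reporting; it does not show that the primary result will be wrong. Pooled adverse-event incidence depends on the enrolment mix whenever the two rates differ, and it may understate first-exposure incidence. Over the assumed range the pooled value is 0.69 to 1.10 times the naïve one with 5 + 7 participants and 0.53 to 1.16 times with 5 + 3. Both ranges cross 1, so neither size nor direction is established. They rest on assumed rate ratios and on up to 5 experienced participants having rolled over.

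Two further gaps need no assumed rate. The SAP does not say whether placebo participants from EDG-5506-001 count as experienced or naïve, although by actual exposure they are first-time users. And the PK split in Protocol 9.4.6 is absent from SAP 3.6 despite the claim of no deviation in section 5.

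**What to change.** Amend SAP 3.4.3, 3.5.1.2, 3.6 and section 5 as follows.

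1. Define prior-exposure status by actual receipt of EDG-5506 in EDG-5506-001, so that placebo roll-overs count as not previously exposed. State in 3.4.3 that this descriptive display is an exception.
2. Show Tables 14.3.1 and 14.3.2.1 to 14.3.2.3 in columns for naïve, experienced and total.
3. Add the same columns for treatment-emergent events with onset in the initial dosing period, before Visit 8. This is the display to read for first-exposure incidence.
4. Show Table 14.4.1.1 by status and restore the Day 1 PK parameters for naïve participants.
5. Add status to the adverse-event listing (16.2.7.1.1).
6. Correct section 5 so that any remaining departure from Protocol 9.4.6 is declared.

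All of this is descriptive, with no tests. It needs no new visits or data: only SAP wording, extra columns, an early-onset display and the Day 1 PK summary. The downside is very small columns with wide intervals, such as 18% to 90% for 4 of 7; showing counts with denominators makes that plain.

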## 3.5 Safety Assessment

All safety analyses will be performed using the SAF unless otherwise noted below.

### 3.5.1 Adverse Events (AEs)

An AE is defined as any untoward medical occurrence in a patient administered a medicinal product. The AE does not necessarily have to have a causal relationship with the study drug. An AE can therefore be any unfavorable and unintended sign (including an abnormal laboratory finding, for example), symptom or disease temporally associated with the use of a medicinal product, whether or not considered related to the medicinal product.

#### 3.5.1.1 General Details

##### Severity

The severity of an AE will be graded, according to the study protocol definitions of AE severity/intensity, as “mild”, “moderate” or “severe”.

##### Related

Each AE relationship to the study drug will be classified as either “related” or “not related”.

Each AE verbatim term will be coded in accordance with the MedDRA® dictionary to a SOC and PT within each SOC. Analysis of AEs will then be performed using SOCs and PTs.

#### 3.5.1.2 AE Summaries

A patient who reported multiple AEs that map to a common PT or SOC is counted only once for that PT or SOC at the highest severity reported and at the greatest relationship to study drug. The number and percentage of subjects who experienced at least one AE will be tabulated by SOC and PT with respect to dose level/treatment group for each study part. The same tabulation will also be applied to any SAE, any AE leading to premature discontinuation from the study, TEAEs and treatment-emergent SAEs.

The number and percentage of patients who experienced at least one AE will also be tabulated by SOC and PT within each dose level/treatment group with respect to relationship to study drug (related, not related) and severity (mild, moderate, severe).

Patient listings will also be provided for all AEs, all SAEs, all AEs leading to early discontinuation from the study and all AEs leading to study drug interruptions. Length of interruptions will also be provided.

An overview of AEs will be provided including counts and percentages of patients with the following:

- Any TEAEs (overall and by maximum severity)
- Any study drug-related TEAEs
- Any serious AEs (SAEs)
- Any TEAEs leading to discontinuation of study drug
- Any TEAEs leading to discontinuation of study

- Any AEs leading to death.

Separate tables including counts and percentages of patients will also be presented by system organ class and preferred term for each of the categories in the overview.

If an AE has incomplete start or stop dates, dates will be imputed to determine whether the AE was treatment-emergent. Details on the imputation for incomplete dates will be provided in the final SAP to correspond to CRF design and instructions.

Patient listings of all AEs will be presented, as well as listings specifically for SAEs and TEAEs leading to discontinuation of study drug.

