2.3.3. Overall Benefit: Risk Conclusion

Considering the measures taken to minimize risk to participants in this study, the potential risks identified in association with EDG-5506 are justified by the anticipated benefits that may be afforded to participants with BMD.

3. Objectives and Endpoints

The study objectives and endpoints are summarized in [Table 2](#).

Table 2 Objectives and Endpoints

Objectives	Endpoints
Primary	

 To assess the safety and tolerability of EDG-5506 in adults with BMD 	
 Incidence, frequency, and severity of AEs and SAEs in those treated with EDG-5506
Secondary	

 To assess the change in individual safety parameters 	
 Incidence of treatment-emergent abnormal laboratory test results (clinical chemistry, hematology, coagulation, and urinalysis) Change from baseline in: 
 Safety laboratory parameters Vital signs Physical and neurological examination ECG parameters Cardiac function as assessed by an echocardiogram Pulmonary function as assessed by FEV₁, FVC C-SSRS

 To assess the PK of EDG-5506 in adults with BMD 	
 PK of EDG-5506
Tertiary/Exploratory	

 To investigate the effect of EDG-5506 on biomarkers of muscle fiber damage in adults with BMD 	
 Change from baseline in: 
 Serum creatine kinase Serum myoglobin Serum cardiac troponin I Plasma troponin I tissue-specific isoforms (fast skeletal, slow skeletal) Serum cardiac troponin T Serum NT-proBNP Plasma SomaScan® proteomics

 To assess the effect of EDG-5506 on functional measures in adults with BMD 	
 Change from baseline in: 
 NSAA NSAD 4-stair climb 100-meter timed test

 To assess the effect of EDG-5506 treatment on self-reported outcomes in adults with BMD 	
 Change from baseline in: 
 PROMIS-57 ACTIVLIM

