9.4.1. General Considerations

Continuous variables will be summarized using the number of observations, mean, standard deviation, median, minimum, and maximum. Categorical variables will be summarized using frequency counts and percentages.

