9.4.2. Safety Analyses

All safety analyses will be made on the Safety Population. Safety data will be summarized in tables and listings.

Adverse events will be coded using the Medical Dictionary for Regulatory Activities (MedDRA). Incidence rates for treatment-emergent adverse events (TEAEs), will be summarized

overall, by maximum severity, and by relationship to EDG-5506. Serious adverse events will also be summarized.

The change from baseline in the following safety endpoints will be summarized at each scheduled assessment time point using descriptive statistics:

- Safety laboratory parameters
- Vital signs
- Physical and neurological examination
- ECG parameters
- LVEF as assessed by cardiac echogram
- Pulmonary function as assessed by FEV₁, FVC
- C-SSRS

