### 2.2 Study Objectives and Endpoints

Primary Objective	Primary Endpoints

To assess the safety and tolerability of EDG-5506 in adults with BMD

	

Incidence, frequency and severity of adverse events (AEs), and serious adverse events (SAEs) in participants treated with EDG-5506

Secondary Objectives	Secondary Endpoints

To assess the change in individual safety parameters

	

Incidence of treatment-emergent (TE) abnormal laboratory test results (clinical chemistry, hematology, coagulation and urinalysis)

Change from baseline (CFB) in:

Safety laboratory parameters

Vital signs

Physical and neurological examinations

Cardiac function, as assessed by electrocardiogram (ECG) parameters

Cardiac function, as assessed by an echocardiogram

Pulmonary function, as assessed

	

by forced expiratory volume in one second (FEV1) and forced vital capacity (FVC)

○ Columbia Suicide Severity Rating Scale (C-SSRS)

• To assess the PK profile of EDG-5506 in adults with BMD

	

• PK concentration levels of EDG-5506

Tertiary/Exploratory Objectives	Tertiary/Exploratory Endpoints

• To investigate the effects of EDG-5506 on biomarkers of muscle fiber damage in adults with BMD

	

• CFB in biomarker measures as assessed by:

○ Serum creatine kinase (CK)

○ Serum cardiac troponin I

○ Serum myoglobin

○ Serum cardiac troponin T

○ Serum N-terminal prohormone brain natriuretic peptide (NT-proBNP)

○ Plasma troponin I tissue-specific isoforms (fast-skeletal, slow-skeletal)

○ Plasma Somascan® proteomics

• To assess the effects of EDG-5506 on functional measures in adults with BMD

	

• CFB in functional assessments, as measured by:

○ NSAA

○ NSAD

○ 4-stair climb

○ 100-meter timed test

○ Muscle strength testing

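### The primary endpoint names AE frequency, but the SAP tables count patients only: add event counts and person-time rates, overall and by dose

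*SAP*

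**What the plan says.** The primary endpoint has three parts. SAP 2.2 gives it as "Incidence, frequency and severity of adverse events (AEs), and serious adverse events (SAEs) in participants treated with EDG-5506", and Protocol Section 3, Table 2 has the same three: "Incidence, frequency, and severity of AEs and SAEs in those treated with EDG-5506". Neither document defines frequency.

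SAP 3.5.1.2 sets the counting rule. A patient with several events in one preferred term (PT) or system organ class (SOC) "is counted only once for that PT or SOC at the highest severity reported and at the greatest relationship to study drug". Numbers and percentages of subjects "will be tabulated by SOC and PT with respect to dose level/treatment group for each study part". The overview table follows the same form: "An overview of AEs will be provided including counts and percentages of patients with the following". The AE table titles in SAP Appendix A (14.3.1 to 14.3.2.5) mention neither a number of events nor a rate.

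Event-level results appear only in listings: "Patient listings of all AEs will be presented, as well as listings specifically for SAEs and TEAEs leading to discontinuation of study drug".

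Protocol 9.4.2 states "Incidence rates for treatment-emergent adverse events (TEAEs), will be summarized", overall, by maximum severity and by relationship, with no time denominator. SAP Section 5 declares no deviation from the protocol's analysis.

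**The concern.** Incidence and severity each have a planned table. Frequency, in the sense of how many events occurred, has none. In the summaries, a participant with one episode of dizziness and a participant with many look the same. If events are counted later from the listings, the counting rule is chosen with the data in view.

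Two features of the design make patient percentages a weak substitute:

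- **Long follow-up.** Treatment lasts up to 24 months, so the share of patients with at least one event can approach 100% for common terms.
- **Unequal observation time.** The dose periods differ in length. SAP 3.3.1 counts a participant who rolls over to the extension before Month 24 as a completer. A percentage with no time denominator then mixes event rate with length of observation.

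At stake is how well the study describes tolerability, its primary objective, and how it compares tolerability across doses.

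**Working it through.** The plan has no figure to reproduce: the sample size is empirical, no test is planned, and no AE rate is stated. The rates below are assumptions, shown as a range.

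**Inputs.** About 8 evaluable participants (Protocol 9.2). Month 24 is the last treatment visit, and months are 30 days (Protocol Table 1 and its note h), so T = 24 × 30 = 720 days = 720/365.25 = 1.97 years for a participant with full follow-up. Dose changes fall at Visits 8, 13 and 21 (SAP 2.4), which are Day 57, Month 6 and Month 15. The periods are therefore 57 − 1 = 56 days, 180 − 56 = 124 days, 450 − 180 = 270 days and 720 − 450 = 270 days, which sum to 720.

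**Step 1: whole study.** For a constant rate L per patient-year, p = 1 − exp(−L × T). Expected events are 8 × L × T. The chance that all 8 are affected is p^8.

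| L per patient-year | % with at least one event | Expected events, n = 8 | Chance of 8/8 affected |
|---|---|---|---|
| 0.1 | 17.9 | 1.6 | <1% |
| 0.25 | 38.9 | 3.9 | <1% |
| 0.5 | 62.7 | 7.9 | 2.4% |
| 1 | 86.1 | 15.8 | 30% |
| 2 | 98.1 | 31.5 | 86% |
| 4 | 99.96 | 63.1 | 99.7% |

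The percentage passes 90% at −ln(0.10)/1.97 = 1.17 per patient-year and 95% at −ln(0.05)/1.97 = 1.52. An observed 8/8 has an exact two-sided 95% lower limit of 0.025^(1/8) = 63%. That corresponds to −ln(1 − 0.63)/1.97, or about 0.5 per patient-year, so 8/8 fits any rate from there upward.

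**Step 2: by dose period.** The same formula, with days/365.25 in place of T, gives the percentage with at least one event:

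| Period | Days | L = 1 | L = 2 | L = 4 |
|---|---|---|---|---|
| 10 mg | 56 | 14.2 | 26.4 | 45.8 |
| 15 mg | 124 | 28.8 | 49.3 | 74.3 |
| 20 mg | 270 | 52.3 | 77.2 | 94.8 |
| 10 mg | 270 | 52.3 | 77.2 | 94.8 |

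At 1 event per patient-year throughout, the percentages differ by 52.3/14.2 = 3.7-fold, solely because the periods differ in length. At 2 per patient-year the ratio is 77.2/26.4 = 2.9.

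**Step 3: what event counts would show.** Full follow-up of 8 participants is 8 × 1.971 = 15.77 patient-years. Event totals are assumed, and the exact Poisson intervals treat events as independent:

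- 8 events: 0.51 per patient-year (95% CI 0.22 to 1.00)
- 32 events: 2.03 per patient-year (1.39 to 2.86)
- 64 events: 4.06 per patient-year (3.13 to 5.18)

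The patient table would be expected to show about 8/8 in both of the last two cases. Recurrence within patients would widen these intervals.

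**The case against.** The strongest reply is that frequency may simply mean a count of patients. Protocol 9.4.1 uses the word that way: "Categorical variables will be summarized using frequency counts and percentages". On that reading, number of patients, percentage of patients and maximum grade cover all three parts. A reader might infer that a primary endpoint component goes unestimated. The documents do not establish that, because the word is undefined. What remains is that the patient-count reading makes frequency repeat incidence, and the number of events still has no planned summary.

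A reader might also take the incidence rates of Protocol 9.4.2 as a promise of person-time rates that the SAP breaks. The text does not support this: summary by maximum severity is a per-patient quantity, and percentages of patients fit it.

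A third tempting reading is that the percentages will saturate. No AE rate is given. Saturation is plausible for any TEAE and for common terms above roughly 1 to 1.5 events per patient-year, but not for uncommon PTs or SAEs at 0.1 to 0.25. Protocol 2.3.1 reports that the common AEs were self-limiting and more frequent early in dosing, so steady recurrence over two years is a simplification. The planned by-dose tables also saturate less: in the 56-day period, a doubling from 2 to 4 per patient-year moves the expected percentage from 26.4% to 45.8%. They remain non-comparable between doses.

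Finally, all AEs are listed, and with about 8 participants a reader could count them. SAP Section 6 places the table shells in separate documents, so their columns cannot be judged here. Both points lower the weight. Neither puts a defined event summary into the SAP.

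**Conclusion.** The point holds as a moderate reporting gap. Frequency as number of events has no planned summary beyond the listings, and the word needs a definition.

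The size depends on the event. Under a constant rate and full 24-month follow-up, the patient percentage is 63% at 0.5, 86% at 1 and 98% at 2 events per patient-year, so it says little about rate for common terms. At 0.1 to 0.25 (18% to 39%) it remains informative. The by-dose comparison is the more practical problem: periods of about 56, 124, 270 and 270 days give percentages up to 3.7-fold apart at an identical 1 event per patient-year. Early rollover adds further imbalance.

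It is not a must-fix. There is no hypothesis test or comparator, no AE-rate threshold is stated, no data are lost, and neither alpha, power nor sample size is affected.

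**What to change.** In SAP 3.5.1.2:

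- **Definition.** Define frequency as the number of events.
- **Tables.** In Table 14.3.1 and the SOC/PT tables for TEAEs, related TEAEs and SAEs, add number of events and events per participant-year next to n (%). Give these overall and by the dose being taken at onset, and add event counts by severity. Deaths and discontinuations do not need them.
- **Assignment to dose.** State how an event with a partial onset date, or with onset during an interruption, is handled. Because 10 mg occurs twice, state whether its two periods are shown separately.
- **Event rule.** State when a worsening of a continuing AE counts as a new event.
- **Person-time.** Use days on study drug, excluding interruptions and any gap between withdrawal and re-enrolment (allowed by Protocol 7.2). The duration formula in SAP 3.3.6, last minus first dose date plus one, removes neither.

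No new data collection is needed: Protocol 6.4 already requires dosing start, stop and delay dates, and SAP 3.1.7 already works from AE onset dates. The cost is a short SAP paragraph, some programming and two extra columns, best settled before database lock. Rates from about 8 participants will be imprecise, and the overall rate will average out early clustering, so it should be read with the by-dose rows.
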